Surveillance will be continued to complete 2 years of follow-up. Blinding will be maintained until the end of the follow-up period. The analysis at the 2 years of follow-up point will still be performed in a blinded manner.

Data Safety Monitoring Plan (DSMP)

All clinical investigations (research protocols testing biomedical and/or behavioural intervention(s)) should include the Data and Safety Monitoring Plan (DSMP). The purpose of DSMP is to provide a framework for appropriate oversight and monitoring of the conduct of clinical trials to ensure the safety of participants and the validity and integrity of the data. It involves involvement of all investigators in periodic assessments of data quality and timeliness, participant recruitment, accrual and retention, participant risk versus benefit, performance of trial sites, and other factors that can affect study outcome.

A Data and Safety Monitoring Plan (DSMP) will be made for the study. It will provide the overall framework for the research protocol's data and safety monitoring. It is not necessary that the DSMP covers all possible aspects of each element. When designing an appropriate DSMP, the following will be kept in mind:

- a) All investigations require monitoring;
- b) The benefits of the investigation should outweigh the risks;
- c) The monitoring plan should commensurate with risk
- d) Monitoring should be performed accounting for the size and complexity of the investigation.

Direct Access to Source Data/Documents

The investigator/institutions will permit (by way of written agreement) trial-related monitoring, audits, IRB/IEC review, and regulatory inspection; providing direct access to source data/documents.

Assessment of Safety

All participants will be informed to contact the vaccination sites during vaccination period or Mirpur treatment centre if the participant requires medical care within 28 days of study agent dosing.

All adverse events which are observed actively or reported/volunteered by subject/guardian will be recorded with information about severity (i.e., whether mild, moderate or severe) and possible relation to the study vaccine by the clinical monitor as described below. The investigator will report adverse events, all abnormal findings, from laboratory and other specific examinations, which are clinically apparent, or in the investigator's opinion clinically significant (Appendices 3A,3C).

In case of any serious adverse events, the investigator should notify the local site IRB, DSMB, IVI and Shantha Biotech immediately by telephone/facsimile/email within 24 hrs and take appropriate measures to safeguard the participants. Every SAE must be reported, even if the Investigator considers that it is not related to the vaccine. The Completed serious adverse event(SAE) form should be submitted to local site IRB/IEC as well as to Shantha's Pharmacovigilance Department within 72 hours either by fax, to the following number: [contact] (to the attention of Pharmacovigilance Department of Shantha) or by email to: [contact]. The causality relationship of the SAE shall be established as mentioned above in the adverse event document section.

A follow-up SAE form must be completed and submitted to Shantha within 24 hours after the Investigator has become aware of any new relevant information concerning the SAE (e.g. outcome, precise description of medical history, results of the investigation).

Copies of documents (e.g., medical records, discharge summary, autopsy) may be requested by the Shantha's PV Department. The anonymity of the subject must always be respected when forwarding this information.

Participants with adverse events shall be followed up till the satisfactory resolution or stabilization with reasonable background of clinical & scientific judgment. Serious adverse events shall be followed up until their resolution.

Irrespective of the investigator's statutory obligations, the sponsor will report all pharmacovigilance data to the competent authorities and to all investigators involved, in accordance with requirements of the ICH Guidelines for Good Clinical Practice as well as local regulatory requirements.

Safety Assessment, Monitoring and Reporting

Neither the bivalent, killed, oral cholera vaccine nor the placebo is known to cause any significant adverse reactions. However, as a precaution, procedures will be in place to detect adverse events in the trial participants as follows: At the vaccination sessions after each dose, recipients will be requested to wait for half an hour at the site, where one staff member will be stationed to monitor any immediate adverse event following vaccination. Individuals with immediate adverse events will receive emergency treatment and the event will be recorded on the form. The adverse event or serious adverse event form will be reported using Medications, Adverse Events, and Serious Adverse Event forms (Appendix 4A, 4B, 4C) and will be reported within 28 days after vaccination whether they are considered vaccine-related or not.

Definition of Adverse event:

An adverse event will be defined as an untoward medical event (diarrhea, vomiting, abdominal pain/cramps or any other local and systemic symptoms) after receipt of a dose which may or may not be

associated with the vaccine. Adverse events will be monitored passively in all participants up to 28 days after vaccination.

Participants will be asked to consult the 'AEFI Case Management Cell' at the icddr,b hospital in Mirpur about any untoward effect after vaccination which will be used as the control room for AEFI management. Assigned physicians, as well as study nurses will be available for 24 hours during the AEFI surveillance period. In addition, support from the existing icddr,b hospital treatment facility will be obtained for AEFI case management. An AEFI committee will be formed for advice and to oversee all reports (Appendix 4A,4B,4C). The 6 member team will include physicians from within the icddr,b hospital and well as those from outside. Necessary medication and emergency services will be available for management of AEFI in the control room. Staff at all other health facilities in the study will report adverse events to the control room at the Mirpur icddr,b hospital. The control room will coordinate and supervise AEFI reporting and management from all the health facilities including the icddr,b Mohakhali hospital. Referral to other hospitals will be made when necessary (for non-diarrheal, acute severe illness requiring specialized care). Emergency ambulance services will also be available for transfer to referral hospitals. Provisions for a preferential case management facility will be provided at the different health centres and compensation will be given when deemed necessary. The compensation will include transportation costs, medication costs, and wage loss.

Active follow up for 28 days in a pre-specified subset of 6,000 study participants will also be carried out. Active surveillance for solicited AEs and all SAEs will be conducted once every two weeks during this month via contact with participants from this cohort. All documentation will be recorded on the previously described AE and SAE forms.

Assessment of Causality

Assessment of an adverse event's relationship to the study drug will be done by a team of medical doctors overseen by the safety monitor of the study and this will be part of the documentation process, but it is not a factor in determining what is or is not reported in the study. If there is any doubt as to whether a clinical observation is a treatment-emergent adverse event, the event should be reported. The relationship of the administration of the study agent to the serious adverse event will be assessed as follows:

- Very Likely/Certain:** A clinical event with a plausible time relationship to vaccine administration and which cannot be explained by concurrent disease or other drugs or chemicals.
- Probable:** A clinical event with a reasonable time relationship to vaccine administration; is unlikely to be attributed to concurrent disease or other drugs or chemicals.

- Possible:** A clinical event with a reasonable time relationship to vaccine administration, but which could also be explained by concurrent disease or other drugs or chemicals.
- Unlikely:** A clinical event whose time relationship to vaccine administration makes a causal connection improbable, but which could be plausibly explained by underlying disease or other drugs or chemicals
- Unrelated:** A clinical event with an incompatible time relationship and which could be explained by underlying disease or other drugs or chemicals.
- Unclassifiable:** A clinical event with insufficient information to permit assessment and identification of the cause.

Assessment of severity of adverse events

The intensity of the adverse event will be rated by the following adapted guidelines [40], applicable to the local context.

Illness or clinical adverse event (as defined according to applicable regulations)	Mild (Grade 1)	Moderate(Grade 2)	Severe (Grade 3)
Fever (°F)	100.4 -101.2	101.3 – 102.1	≥102.2
Nausea/vomiting	No interference with activity or 1 – 2 episodes/24 hours	Some interference with activity or > 2 episodes/24 hours	Prevents daily activity, requires IV hydration
Diarrhea	2 – 3 loose stools or < 400 gms/ 24 hours	4 – 9 stools within 24 hour	10 or more watery stools within 24 hours or requires IV hydration
Headache	No interference with activity	Some interference with activity or repeated use of non-narcotic pain reliever	Significant, prevents daily activity or repeated use of narcotic pain reliever
Fatigue	No interference with activity	Some interference with activity	Significant, prevents daily activity
Myalgia	No interference with activity	Some interference with activity	Significant, prevents daily activity

Changes in the severity of an adverse event will be documented to allow an assessment of the duration of the event at each level of intensity. Adverse events characterized as intermittent will require documentation of onset and duration of each episode.

Definition of Serious Adverse Event

A serious adverse event (experience) is any untoward medical occurrence that results in death or is life-threatening. The term “life-threatening” in the definition of “serious” refers to an event in which the

recipients will be at risk of death at the time of the event; it does not refer to an event, which hypothetically might have caused death, if that were more severe.

A serious adverse event (SAE) is defined as an AE meeting one of the following conditions:

- Death during the period of protocol-defined surveillance
- Life-threatening event (defined as a study participant at immediate risk of death at the time of the event)
- An event requiring hospitalization or prolongation of existing hospitalization during the period of protocol-defined surveillance. In case of diarrhea, an SAE will be one that requires admission to an inpatient ward for >24 hours.
- Results in congenital anomaly or birth defect, or malignancy
- Results in a persistent or significant disability/incapacity

Any other important medical event that may not result in death or be life threatening, may be considered a serious adverse event when, based upon appropriate medical judgment, the event may jeopardize the study participant and may require medical or surgical intervention to prevent one of the outcomes listed above. Prudent medical judgment must be exercised to decide whether reporting is appropriate.

Reporting Procedures of Serious Adverse Events

All SAEs that occur during the study will be reported by study PI or designee within 24 hours to the ERC and the DSMB as well as to IVI and ShanthaBiotechnics. The SAE form will always be completed as thoroughly as possible with all available details of the event, signed by the principal investigator. If the investigator does not have all the information regarding an SAE, he/she will not wait to receive additional information before submitting the report. If deemed necessary, the DSMB will have the authority to call a temporary suspension of the study, for careful review and assessment of the reported event(s). The study physicians/medical officers will follow-up the participants with SAEs until the event has: resolved, subsided, stabilized or disappeared or the event is otherwise explained, or the participant is lost to follow-up. The date of final disappearance of the adverse event will be documented. The study physician will always provide an assessment of causality at the time of the initial report.

Ethical Assurance for Protection of Human rights

Describe the justifications for conducting this research in human participants. If the study needs observations on sick individuals, provide sufficient reasons for using them. Indicate how participants' rights will be protected, and if there would be benefit or risk to each participants of the study. Discuss the ethical issues related to biomedical and social research for employing special procedures, such as invasive procedures in sick children, use of isotopes or any other hazardous materials, or social questionnaires relating to individual privacy. Discuss procedures safeguarding participants from injuries resulting from study procedures and/or interventions, whether physical, financial or social in nature. [Please see Guidelines]

The Nuffield Council of Bioethics recommends that “wherever appropriate, participants in the control group should be offered a universal standard of care for the disease being studied. Where it is inappropriate to offer such a standard, the minimum that should be offered is the best intervention currently available as part of the national public health system”[38][45]. While some critics may argue that the standard of care should be the “best method”, Wendler, et al suggested four conditions when the standard of care may be less than a universally accepted “best method” and these conditions include: a) scientific necessity; b) the relevance of the study for the host community should address important health issues of the communities participating in the studies; c) the need for the clinical trial to produce a fair level of benefit for the communities participating in the trial; and d) subject and host community non-maleficence i.e., the study participant must not be “prospectively worse off” than they would if the trial were not conducted [39]. This study fulfils all four criteria. There is a scientific necessity to perform the trial; the study is of relevance to the communities to be included in the trial as the population has high rates of cholera (areas will be chosen based on previously reported cholera cases in the hospital surveillance being performed by icddr, b) and the community will benefit from the surveillance activity that not only does diarrhoea surveillance but at the same time promotes safe water and sanitation practices. Medical care will be provided for any medical ailment or injury that occurs to any participant that is likely due to the study agent. Appropriate ethical and regulatory clearances will be obtained prior to the trial. Once the vaccine is approved for the single dose indication, provisions to make the cholera vaccine available to placebo recipients will be made.

The study will be conducted in compliance with the procedures outlined in this protocol and in accordance with the ethical guidelines and local regulatory requirements for the trial. The investigators’ responsibilities will follow the WHO guidelines for GCP. The privacy and confidentiality of all data and information collected from the trial participants, including those derived from clinical and biological specimens, will be ensured both during and after the conduct of the trial. Individuals will not be identified in any reports and publications based on the trial data.

Verbal and written informed consent will be obtained prior to intervention from eligible adult participants and the parents/guardians of participants aged <18 years; in addition, assent will be obtained from children aged 11-17 years of age (see Informed Consent form), Consent and assent will be documented by signature or thumbprint on the appropriate forms and noted down in the Vaccination Record. Participants and parents/guardian of the child will be informed of the study activities, and they will be encouraged to ask questions regarding the study. Signature (or thumbprint, if illiterate) of the participants and parents/guardian of the child will be obtained before their enrollment in the study and dated prior to any study-related activity. A witness will also sign in the informed consent form in the

event a participant, parents/guardian of a child participant, is not literate. The informed consent form must be signed and dated by the study personnel who obtain the consent. In addition informed consent will be obtained from 324 participants who agree to have blood taken at two time points following dosing during the study period. Verbal consent will be obtained from participating subjects who will be followed by active surveillance for safety and also from those who will be monitored for pregnancy outcomes.

If new information, not covered in the proposal, on the study product becomes available that may be relevant to the participants' willingness to continue in the study, the investigator will inform that in a timely manner and use a revised written informed consent form. The proposal will be revised and resubmitted to RRC and ERC for the amendment and will then be used for obtaining permission.

The expected duration of subject participation

The duration of follow-up for each participant will be 24 months after dosing.

A description of "stopping rules" or "discontinuation criteria" for individual participants, parts of the trial and the entire trial

The study is planned for the duration of 2 years of follow up after vaccination. Primary analysis will be conducted at 6 months, with secondary analyses conducted at 12, 18 and 24 months of follow up. Efficacy results will be submitted to the DSMB following primary and interim results.

The trial may be stopped for ethical reasons

at the recommendation of IRB of any of the partner institutions or for the safety reasons at the recommendations of the DSMB and collaborating institutes.

Use of Animals

Describe if and the type and species of animals to be used in the study. Justify with reasons the use of particular animal species in the research and the compliance of the animal ethical guidelines for conducting the proposed procedures.

NA

Collaborative Arrangements

Describe if this study involves any scientific, administrative, fiscal, or programmatic arrangements with other national or international organizations or individuals. Indicate the nature and extent of collaboration and include a letter of agreement between the applicant or his/her organization and the collaborating organization.

This project is a collaborative study of icddr, b, the International Vaccine Institute (IVI) in Korea, and Shantha Biotechnics in India as well as other international and national experts in the field of vaccines .

Facilities Available

Describe the availability of physical facilities at site of conduction of the study. If applicable, describe the use of Biosafety Level 2 and/or 3 laboratory facilities. For clinical and laboratory-based studies, indicate the provision of hospital and other types of adequate patient care and laboratory support services. Identify the laboratory facilities and major equipment that will be required for the study. For field studies, describe the field area including its size, population, and means of communications plus field management plans specifying gender considerations for community and for research team members.

A large area based on updated GIS maps is available in high cholera prone field site at Mirpur urban area in Dhaka. Diarrheal hospitals of icddr, bin Mohakhali and Mirpur and existing health facilities as well as laboratory facilities are available for the study.

Literature Cited

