We will use the killed whole cell oral cholera vaccine, Shanchol™ as well as an oral placebo for the study. The vaccine is manufactured by Shantha Biotechnics, in Hyderabad, India and registered in India and is prequalified by the WHO. Shanchol™ is available in a single dose vial. The study agents will be supplied by the company and imported by approaching the Directorate General of Drug Administration of Bangladesh. Both the vaccine and placebo will be transported from the manufacturer to a designated EPI cold room at Mohakhali, Dhaka arranged for this study where it will be stored. We will identify vaccination centers within the intervention areas. These sites may include the government's EPI outposts, non-government facilities utilized during national immunization days, or other appropriate facilities which are easily accessible by the target population (Appendix 1C). Study agents will be maintained at 2-8°C. Immunization will be carried to the study population in three phases. Vaccination teams composed of the required number of vaccinators, record keepers, consent takers, supervisors, and other support staff will be present at each vaccination site (approximately 30 sites). Each participant over

the age of one year and non pregnant females living in communities will be individually randomized to receive vaccine or placebo.

Pregnancy status will be enquired verbally for all married women of child bearing age during the census update as well as before vaccination to exclude them from the study. If she is uncertain about her pregnancy status, she will be asked for her last menstrual period (LMP). All married females will be asked about their last LMP, if this is more than four weeks prior, irregular, or unknown, will be considered ineligible for the study. Pregnancy status in married women will also be ascertained at least two months after vaccination by home visits of trained field staff. Those who will be confirmed for pregnancy at this time point will be followed up at 6 months as well as with further visits monthly to ascertain pregnancy outcome after delivery. A pregnancy followup questionnaire will be used after consent taking for these visits (Appendix 6A, 6 B).

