The agent to be received by the participants will be determined by the randomization number on the vial. Vials will be consecutively numbered, but individually randomized into the vaccine or placebo arm. After shaking the vial properly, it will be opened and given to the participant. The contents will be poured into the mouth by the recipient, followed by intake of a small volume of water. We shall allow the participant to take the study agent by themselves for those who are 5 years and older. For younger children, the vaccine will be given by the vaccinator. At the time of the dosing, completeness of dosing will be observed and this information will be documented. Vials used for the administration of the vaccine and placebo will be disposed by incineration. The records of the vaccine and placebo usage and destruction will be maintained in the study file and also shared with the manufacturer for reconciliation.

Selection and Withdrawal of Participants

Inclusion criteria:

All healthy, consenting, non-pregnant (as ascertained by history) residents of a high risk group, at least 1 year of age, of the study area will be included in the trial.

Exclusion criteria:

The following will be excluded from the trial:

- Pregnant women (identified through verbal screening);
- Aged less than 1 year
- History of intake of any cholera vaccine

Participants may withdraw from the study at any point. The data collected for withdrawn participants, in addition to standard questionnaire data, will include the reason for withdrawal. No additional follow-up is envisioned for withdrawn participants.

Accountability procedures for the investigational product, including the comparator:

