The DSMB will also be responsible for un-blinding the randomization number codes in the event of severe putative vaccine reactions. Otherwise, the codes will not be revealed until the end of the trial and until the computerized dataset has been frozen. If the intervention assignment is un-blinded, all study collaborators will be notified immediately.

Measurements

Census update

The census in the study population will be updated every six months after intervention with the study agents. During this process in-migrants within the study area will get a SCVB card with unique ID to ease the disease surveillance process. Data collectors will visit each house in the intervention areas and collect information on births, deaths, migrations (in/out), missed in previous census, change in marital status, pregnancies and other events (Appendix 1D).

Disease Surveillance

1. Surveillance at the icddr,b hospitals in Mohakhali and Mirpur

All patients from the study area presenting for care at the hospital with diarrhea will be included in routine hospital surveillance. A diarrhoeal visit is defined as a visit by a patient who has in the 24 h before presentation, three or more loose or liquid stool or at least 1 bloody loose stool or any number of loose stools with signs of dehydration present, as stated in criteria used at the icddr,b hospitals[29]. The assessment of dehydration status in diarrhea will be carried out by trained personnel.

The diarrheal disease surveillance for the project will be conducted at icddr,b hospitals at Mohakhali and Mirpur and other health facilities for patients coming from the Mirpur study area (wards 7-13, 15 and 41). Clinical staff at each of the two hospitals and other facilities will evaluate each patient at the hospital triage area and provide treatment as per the routine procedure. Internal clinical monitoring for quality control will also be carried out for hospitalized study patients using a disease surveillance questionnaire (Appendix 2B). Around 5% of the study patients will be further evaluated immediately after admission. A trained physician will function as the safety monitor for the study and will oversee

clinical procedures for patient enrolment and management during surveillance to monitor GCP practice and trial conduct.

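### Pregnancy exclusion covers all women, but the detailed screening and post-dose check name only married women, and no stated step sends pregnancies or births found at census updates into outcome follow-up

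*Supplement*

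**What the plan says.** All references are to the latest protocol unless stated.

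- **Eligibility** (Selection and Withdrawal of Participants). Inclusion: "All healthy, consenting, non-pregnant (as ascertained by history) residents of a high risk group". Exclusion: "Pregnant women (identified through verbal screening". Neither has a marital limit. The data analysis plan, section 2, also requires subjects not to be pregnant and adds no procedure.
- **Pre-dose enquiry** (Delivery of study agent): "Pregnancy status will be enquired verbally for all married women of child bearing age during the census update as well as before vaccination".
- **LMP rule** (same section): "All married females will be asked about their last LMP". A last period more than four weeks ago, irregular or unknown makes the woman ineligible.
- **Post-dose check** (same section): "Pregnancy status in married women will also be ascertained at least two months after vaccination", by home visit.
- **Entry to outcome follow-up** (same section): "Those who will be confirmed for pregnancy at this time point will be followed up at 6 months", then monthly until the outcome after delivery is known.
- **Census update** (Measurements): "The census in the study population will be updated every six months after intervention with the study agents". "Data collectors will visit each house in the intervention areas and collect information on births, deaths, migrations (in/out". Change in marital status and pregnancies are on the same list. The section does not say who is asked about pregnancy, or what is done when one is found.
- **Serious adverse events**: a congenital anomaly or birth defect is serious in any participant, and all serious events are to be reported within 24 hours.

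**The concern.** There are two gaps.

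First, the exclusion applies to all women, while the procedure that puts it into effect is written for some of them. A married woman whose last period was five weeks ago is ineligible under the LMP rule. A widowed, divorced or separated woman with the same history could be dosed if she does not report a pregnancy when her general history is taken. She would also have no home check two months later. The documents give no reason for treating the two women differently.

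Second, follow-up to pregnancy outcome has one stated entrance, the check at two months or later. A married woman who is away or missed at that visit, or a woman never due for it, may have a pregnancy or birth recorded at a later census update. No sentence sends that record into follow-up.

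What is at stake is even, systematic follow-up of pregnancies exposed to the study agent. The protocol evidently values this, since it plans monthly visits until the outcome is known.

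**Working it through.** **1. Text side by side**

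| Step | Who is covered, as written |
|---|---|
| Eligibility by history or verbal screening | Everyone |
| Enquiry at census update and before dosing | Married women of child-bearing age |
| LMP ineligibility rule | Married females |
| Home check at two months or later | Married women |
| Entry to outcome follow-up | Women confirmed pregnant at that check |
| Later census updates | Each house; who is asked about pregnancy is not stated |
| Serious-event reporting | Any participant |

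The marital limit appears at all three detailed steps, so it reads as a stated scope and not a slip. No row links the census updates to outcome follow-up.

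**2. What the sample size says about pregnancy**

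Inputs (Sample size calculation for primary analysis): 191,660 to be analysed, 6.25% attrition over six months, 65% participation, 2% under one year, 1% pregnant.

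- Vaccinated: 191,660 / (1 − 0.0625) = 204,437 (stated 204,438).
- Enumerated: 204,437 / (0.65 × 0.98 × 0.99) = 324,180 (stated 324,178).

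The plan's figures reproduce to rounding. Its 1% therefore applies to the enumerated population after infants are removed: 324,178 × 0.98 × 0.01 = 3,177 pregnant women of any marital status.

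**3. How many are outside the detailed procedure**

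This cannot be derived, because no split by marital status is given. As an illustration only, assume that 0.5% to 2% of these pregnancies are in women not currently married:

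- 3,177 × 0.005 = 16 and 3,177 × 0.02 = 64.
- At 65% participation: 16 × 0.65 ≈ 10 and 64 × 0.65 ≈ 41 coming forward, about half of them allocated vaccine.

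The assumed share is not bounded by anything in the documents, so 41 is not a ceiling. The general history would also exclude some of these women before dosing.

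**4. Effect on efficacy**

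This check does not need the assumed share. Suppose all 3,177 pregnancies escaped screening: 3,177 × 0.65 = 2,065 women, and at the placebo incidence of 0.56 per 1,000 over six months, 2,065 × 0.00056 = 1.2 cases. The plan expects 95,830 × 0.00056 + 95,830 × 0.00028 = 53.7 + 26.8 = 80.5 cases. At the illustrative 41 women the figure is 41 × 0.00056 = 0.02 cases. With random allocation, neither matters.

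**5. Why births must be included in any link**

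Take an update 26 weeks after dosing and a 40-week pregnancy (assumed). A woman at 40 − 26 = 14 weeks or more at dosing would have reached term by then. A link restricted to current pregnancies would miss her.

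**The case against.** The strongest reply is that a general rule with a stricter procedure for one group is no contradiction. Everyone must be non-pregnant by history, and the LMP rule and home visit are extra care where most pregnancies will occur. Direct questions to unmarried women may also be unwelcome locally. This stands in part: the exclusion does reach everyone, and how to question never-married women is for local judgement. It does not explain why widowed, divorced and separated women are left out, and a general history provides neither a post-dose check nor an entrance to follow-up.

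A second reply is that the link may sit in forms that are not shown: the census-update form (Appendix 1D) and the pregnancy follow-up forms (Appendices 6A and 6B). The superseded version 1.0 protocol used Appendix 1D as the notification for any pregnant woman vaccinated by accident. That sentence is absent from the latest text, so it does not establish a current route, but the possibility remains open.

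A reader might infer more than the text supports:

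- *That women outside the married group are not screened at all.* The eligibility criteria require a history from every participant.
- *That harm in an exposed pregnancy would go unreported.* Birth defects and other serious events are reportable for any participant. The gap is in systematic follow-up; serious-event reporting still depends on the outcome coming to staff attention, and routine adverse-event monitoring runs for 28 days.
- *That the census updates already identify every pregnancy.* The census-update section does not say who is asked, and the only stated enquiry at a census update names married women. For never-married women the updates may reveal births only.

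**Conclusion.** The point holds as a minor safety matter. The detailed screening and post-dose check have a narrower scope than the exclusion they serve, leaving widowed, divorced and separated women to the general history alone. Outcome follow-up has one described entrance, so a pregnancy or birth first found at a census update has no stated route into it, whatever the participant's marital status.

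The number affected is unknown and probably small. The conclusion rests on the plain meaning of *married* and on the text shown; the appendix forms could narrow the second gap. Efficacy, sample size and the primary analysis are not affected. This is a cheap improvement, not a condition for the trial to be sound.

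**What to change.** 1. Under Delivery of study agent, replace *married* with *ever-married (including widowed, divorced and separated)* in the pre-dose enquiry, the LMP rule and the two-month home check.
2. Under Measurements, Census update, add: *Any pregnancy or birth in a participant that is found at a census update and dated to before dosing enters the pregnancy follow-up described under Delivery of study agent, whatever the marital status.*

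For never-married women the second change may catch births only. Whether to ask them directly should be decided locally and the decision recorded. If Appendix 1D, 6A or 6B already holds this route, a cross-reference is enough.

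The cost is slightly more field work at visits that already take place. The consent section already provides verbal consent for those monitored for pregnancy outcomes, with no marital limit.
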